10.1 General principles

A subject may withdraw from the trial (prior to first dose or during the treatment period) or permanently discontinue trial treatment at any time if the subject, the investigator, or LEO Pharma considers that it is not in the subject's best interest to continue.

To obtain the most representative efficacy and safety evaluation of brodalumab in the target population, the subject will be asked to remain in the trial and complete all the remaining visits and assessments after permanent discontinuation of IMP. It is key to assess the efficacy status of each subject at the planned primary endpoint visit (Week 16, see Section 4) irrespective of whether the subject has discontinued IMP or not. Therefore, the permanent discontinuation of IMP is evaluated as a separate occurrence that does not necessitate withdrawal from the trial.

Permanent discontinuation of IMP and withdrawal from trial are considered 2 (potentially) separate occurrences:

- Permanent discontinuation of IMP occurs when all **further trial treatment** is stopped. The subject will continue to participate in trial visit activities as outlined in Section 10.3.
- Withdrawal from trial occurs when all **further trial activities** are stopped before the final visit at Week 28. This can happen either at the same time as permanent discontinuation of IMP or later.

Medical reasons for discontinuation of IMP are given in Section 10.2.1.

Reason(s) for discontinuation from IMP and/or withdrawal from the trial must be recorded in the medical records and the eCRF (lack of efficacy, AE, withdrawal by subject, lost to follow-up, death, pregnancy, or other, Sections 10.2.1 and 11.6.2). For subjects randomised to IMP, but not attending any post-baseline visits, it will be recorded whether any safety evaluations were performed after exposure to IMP.

Subjects who withdraw from the trial and subjects who discontinue IMP will not be replaced.

If a subject withdraws from the trial, he or she may request destruction of any samples taken and not tested, and the investigator must document this in the subject's trial records.

THIS DOCUMENT CONTAINS CONFIDENTIAL INFORMATION AND MUST NOT BE COPIED OR MADE AVAILABLE TO ANY THIRD PARTY WITHOUT THE PRIOR WRITTEN CONSENT OF THE LEO PHARMA GROUP

10.2 IMP discontinuation rules

10.2.1 Reasons for permanent discontinuation of IMP

When discontinuing IMP, either at the scheduled end-of-treatment visit or IMP is discontinued prematurely, the subject should be treated at the discretion of the investigator (Section 9.9).

Subjects will permanently discontinue IMP prematurely in the event of:

- Having shown no response (efficacy) after 16 weeks of treatment.
- Anaphylactic reaction or other severe systemic reaction to IMP injection.
- An AE or deterioration of an AE that, in the opinion of the investigator or sponsor's medical expert, contraindicates further IMP administration (e.g. Crohn's disease).
- Some cases of use of prohibited medication and treatment, see Section 9.7 for further details.
- Diagnosis of a malignancy during the trial, excluding carcinoma in situ of the cervix, or localised squamous or basal cell carcinoma of the skin.
- Evidence of pregnancy (positive serum pregnancy test).
- Any infection that is opportunistic, such as active tuberculosis and other infections whose nature or course may suggest an immunocompromised status.
- Any suicidal behaviour or suicidal ideation of category 4 or 5 according to the C-SSRS (the subject must be referred to a mental health professional).
- A PHQ-8 score of ≥ 15 corresponding to moderately severe-to-severe depression (the subject must be referred to a mental health professional).
- Any single measurement of ANC $< 0.50 \times 10^3/\mu\text{L}$.
- Severe laboratory abnormalities:
 - ALT and/or AST values $> 3 \times \text{ULN}$ with total bilirubin $> 2 \times \text{ULN}$ (unless elevated bilirubin is related to Gilbert-Meulengracht Syndrome).
 - Confirmed ALT and/or AST $> 5 \times \text{ULN}$ (for more than 2 weeks).

Refer to Section 10.3 for details on the handling of discontinuation of IMP or withdrawal of a subject, and to Section 4 for assessments to be performed in case of discontinuation of IMP.

THIS DOCUMENT CONTAINS CONFIDENTIAL INFORMATION AND MUST NOT BE COPIED OR MADE AVAILABLE TO ANY THIRD PARTY WITHOUT THE PRIOR WRITTEN CONSENT OF THE LEO PHARMA GROUP

Data to be recorded in the eCRF

The primary reason for permanent discontinuation of IMP must be recorded in the medical records and on the end-of-treatment form in the eCRF where the following options are available:

- Lack of efficacy.
- Adverse event.
- Withdrawal by subject.
- Lost to follow-up.
- Death.
- Pregnancy.
- Other.

If ‘other’ is selected, a specification must be provided in the eCRF. If ‘adverse event’ is selected, the AE in question will be linked to the IMP discontinuation.

‘Lack of efficacy’ should be assigned when a subject experiences aggravation/exacerbation/worsening of the trial disease, even when it is documented as an (S)AE according to Section 13.6.5.

10.2.2 Reasons for temporary discontinuation of IMP

Administration of IMP should be temporarily suspended in the event of:

- An infection that requires parenteral treatment with antibiotic, antifungal, antiviral, anti-parasitic, or anti-protozoal agents. The administration of the IMP should be withheld until the infection has resolved in the opinion of the investigator.
- Other major intercurrent illnesses or major surgery. The administration of the IMP should be withheld until the event has resolved in the opinion of the investigator.
- ANC $\geq 0.50 \times 10^3/\mu\text{L}$ to $\leq 1.5 \times 10^3/\mu\text{L}$ and fever. The administration of the IMP should be withheld until the infection has resolved in the opinion of the investigator and ANC is $> 1.5 \times 10^3/\mu\text{L}$.
- Positive urine pregnancy test. The administration of the IMP should be withheld until confirmation by serum pregnancy test.

THIS DOCUMENT CONTAINS CONFIDENTIAL INFORMATION AND MUST NOT BE COPIED OR MADE AVAILABLE TO ANY THIRD PARTY WITHOUT THE PRIOR WRITTEN CONSENT OF THE LEO PHARMA GROUP

A decision to discontinue IMP temporarily or to reinstitute IMP treatment must be discussed with sponsor's medical expert. However, the investigator may suspend trial treatment at any time, even without consultation with sponsor's medical expert if the urgency of the situation requires immediate action and if this is determined to be in the subject's best interest. In such cases, sponsor's medical expert should be informed as soon as possible. The schedule of planned visits should be maintained and all trial-related assessments should still be performed during the period of temporary discontinuation of IMP.

If all assessments were performed prior to IMP administration, but a decision was made to temporarily discontinue IMP, the IMP should be administered at a rescheduled visit, which should be reported in the eCRF as an unscheduled visit. The subsequent IMP administration should be scheduled according to the schedule of the trial procedures with a minimum of 7 days to the subsequent administration of the respective IMP (visits 3 and 4 are exempt from the 7-day gap requirement). When IMP is temporarily discontinued on a visit where 2 injections are required, the 2 injections can be rescheduled independently due to the difference in administration frequencies (brodalumab/dummy 2: Q2W, guselkumab/dummy 1: Q8W). If the trial visit cannot be rescheduled to maintain a minimum of 7 days to the subsequent scheduled dose, the sponsor's medical expert should be contacted.

10.3 Early termination assessments

Permanent discontinuation of IMP

Unless the subject discontinues IMP due to withdrawal of consent, lost to follow-up, or death, subjects will be encouraged to continue in the trial for collection of scheduled efficacy and safety assessments, or at least attend an early termination visit and primary endpoint visit as indicated below (see Section 4 for data to be collected at these visits). The investigator will review any AEs which will be followed up according to Section 13.7, if the subject agrees.

Subjects who permanently discontinue IMP prior to Week 16 (Visit 11) will be asked to attend at least:

- Early termination visit, as soon as possible and within 2 weeks of the last IMP administration.
- Primary endpoint assessment visit at nominal Week 16 (Visit 11).

Subjects who permanently discontinue IMP at Week 16 (Visit 11) or hereafter will be asked to attend at least:

- Early termination visit, as soon as possible and within 2 weeks of the last IMP administration.

THIS DOCUMENT CONTAINS CONFIDENTIAL INFORMATION AND MUST NOT BE COPIED OR MADE AVAILABLE TO ANY THIRD PARTY WITHOUT THE PRIOR WRITTEN CONSENT OF THE LEO PHARMA GROUP

Withdrawal from trial

Subjects who withdraw from the trial for any reason will be asked to attend an early termination visit as soon as possible after last administration of IMP. See the schedule of trial procedures (Section 4) for data to be collected. The investigator will review any AEs which will be followed-up according to Section 13.7, if the subject agrees.

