The primary estimand for continuous endpoints based on subject assessments can be seen to assess the LS-mean difference in the continuous endpoint regardless of permanent discontinuation of IMP, if permanent discontinuation of IMP due to pandemic restrictions and unblinding of subjects would not occur. In accordance with [Panel 21](#), this estimand will address unblinding of subjects by the same 'hypothetical' strategy as used for addressing permanent discontinuation of IMP due to pandemic restrictions. This means that the above elaboration on estimand strategy also applies to the primary estimand for continuous endpoints based on subject assessments with the exception that unblinding of subjects will be handled just as permanent discontinuation of IMP due to pandemic restrictions.

THIS DOCUMENT CONTAINS CONFIDENTIAL INFORMATION AND MUST NOT BE COPIED OR MADE AVAILABLE TO ANY THIRD PARTY WITHOUT THE PRIOR WRITTEN CONSENT OF THE LEO PHARMA GROUP

Main analysis

Each of the 1000 imputed datasets will be analysed based on an ANCOVA model, including baseline body weight (≤ 100 kg and >100 kg), prior TNF- α inhibitor use at baseline (≤ 1 , >1) and treatment arm as factors and adjusting for the baseline value of the endpoint as a covariate. The pooled estimate of the difference in the LS-mean between the brodalumab and guselkumab arms, along with the associated 95% CIs and nominal p-values, will be presented based on applying Rubin's rules to the estimates and standard errors from the aforementioned ANCOVA analysis of the imputed datasets.

Sensitivity analyses

Rather than assuming missing data are MAR, the sensitivity analyses will impute missing data based on the following algorithms:

- ‘Delta-adjusted’ pattern-mixture model.
- ‘Retrieved-data’ pattern-mixture model (if sufficient data exist).

Missing data arising after the occurrence of intercurrent events to be addressed by a ‘hypothetical’ strategy cf. [Panel 21](#) will not be imputed by the algorithms mentioned above, as the value of the estimand’s variable will be determined by the strategy for addressing the intercurrent event.

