The primary estimand associated with this endpoint can be seen to assess the LS-mean difference in absolute PASI at Week 16 regardless of permanent discontinuation of IMP and subjects becoming unblinded, if permanent discontinuation of IMP due to pandemic restrictions would not occur. In the following, we elaborate on the estimand strategy described in [Panel 17](#) for this estimand, specifically the ‘hypothetical’ strategy for addressing permanent discontinuation of IMP due to pandemic restrictions.

The hypothetical scenario envisaged is that permanent discontinuation of IMP due to pandemic restrictions would not occur and that subjects who have experienced this event would respond like similar subjects who have not experienced it. Data collected after permanent discontinuation of IMP due to pandemic restrictions will be excluded. The ‘hypothetical’ strategy and the handling of missing data in the main analysis are outlined in [Panel 18](#).

Panel 18. ‘Hypothetical’ strategy for addressing permanent discontinuation of IMP due to pandemic restrictions and handling of missing data in the main analysis of the primary estimand for ‘Absolute PASI at Week 16’

Step no.	Description	Subjects in scope for imputation	Purpose
1	Impute PASI score at Week 16 under MAR assumptions	Subjects who have permanently discontinued IMP due to pandemic restrictions prior to Week 16	‘Hypothetical’ strategy
		Subjects who have not permanently discontinued IMP due to pandemic restrictions prior to Week 16 and whose score at Week 16 is missing	Handling of missing data

Abbreviations: IMP = investigational medicinal product; MAR = missing at random; PASI = Psoriasis Area and Severity Index.

The imputation of PASI scores at Week 16 will be carried out as specified for the primary

THIS DOCUMENT CONTAINS CONFIDENTIAL INFORMATION AND MUST NOT BE COPIED OR MADE AVAILABLE TO ANY THIRD PARTY WITHOUT THE PRIOR WRITTEN CONSENT OF THE LEO PHARMA GROUP

estimand for the primary endpoint. The elaborations above are based on the endpoint ‘Absolute PASI at Week 16’, but the same principles will be applied for the primary estimand associated with other continuous endpoints based on investigator assessments.

Continuous endpoints based on subject assessments

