The primary estimand for continuous endpoints based on subject assessments can be seen to assess the LS-mean difference in the continuous endpoint regardless of permanent discontinuation of IMP, if permanent discontinuation of IMP due to pandemic restrictions and unblinding of subjects would not occur. In accordance with [Panel 17](#), this estimand will address unblinding of subjects by the same ‘hypothetical’ strategy as used for addressing permanent discontinuation of IMP due to pandemic restrictions. This means that the above elaboration on estimand strategy also applies to the primary estimand for continuous endpoints based on subject assessments with the exception that unblinding of subjects will be handled just as permanent discontinuation of IMP due to pandemic restrictions.

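### Week 28 is requested but not in the minimum visit set after stopping IMP, although the Week 28 continuous endpoints need off-treatment values

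*Protocol*

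**What the plan says.** **Visits after stopping IMP.** Protocol Section 10.1 gives the general rule: "the subject will be asked to remain in the trial and complete all the remaining visits and assessments after permanent discontinuation of IMP". Section 10.3 begins in the same direction, saying that "subjects will be encouraged to continue in the trial for collection of scheduled efficacy and safety assessments, or at least attend" two named visits, one for early termination and one for the primary endpoint. Two minimum lists follow. A subject who stops before Week 16 is asked for the early termination visit and the Week 16 visit. For the others the text reads "Subjects who permanently discontinue IMP at Week 16 (Visit 11) or hereafter will be asked to attend at least", and the list has a single entry, the early termination visit within 2 weeks of the last administration. Note 2 to Panels 2 and 3 and note 3 to Panel 29 likewise single out Week 16 and not Week 28. Section 10.2.1 includes among the reasons for permanent discontinuation "Having shown no response (efficacy) after 16 weeks of treatment".

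**Estimands.** For continuous endpoints, protocol Section 14.3.6.4 and SAP Section 5.4.3 use a treatment-policy strategy for discontinuation independent of pandemic restrictions. The worked example for investigator assessments is the "LS-mean difference in absolute PASI at Week 16 regardless of permanent discontinuation of IMP and subjects becoming unblinded", and its principles carry over to the other continuous investigator endpoints. For subject assessments the protocol defines the effect "regardless of permanent discontinuation of IMP, if permanent discontinuation of IMP due to pandemic restrictions and unblinding of subjects would not occur". SAP Panel 10 lists change in SF-36v2 PCS and MCS at Week 28 as secondary and absolute PASI at Week 28 as exploratory.

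**Missing values.** They are imputed under MAR within randomised arm (SAP Sections 5.4.1 and 5.4.3). The protocol also planned a retrieved-data pattern-mixture analysis if data sufficed. SAP Section 6 drops it because the trial ends ahead of schedule. The delta-adjusted analysis remains (SAP Sections 5.4.3.2 and 5.4.1.2.1), with one margin for both arms.

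**The concern.** A treatment-policy estimand at Week 28 includes the outcome of subjects who are no longer on IMP, so their Week 28 value is part of the target. The visit rules ask for that value but let a subject fall back to a set that does not contain it.

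SF-36v2 is the most exposed, because after Week 16 it is scheduled only at Week 28. A subject who stops at Week 16 and takes the fallback has a last SF-36v2 at Week 16, or by Week 18 if the early termination visit falls 2 weeks after a Week 16 dose. That is 10 to 12 weeks before the endpoint.

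The imputation model is fitted to the whole arm without separating subjects on and off IMP. The analysis that would have separated them draws on subjects who stop IMP and stay in the trial, which is the group the minimum set does not secure for Week 28.

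At stake are one secondary endpoint family and one exploratory endpoint at a single time point, not the main result.

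**Working it through.** **1. Which endpoints depend on a Week 28 value from a subject off IMP** (SAP Panels 10, 11, 14 and 17; discontinuation independent of pandemic restrictions):

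| Endpoint | Strategy | Off-IMP Week 28 value used? |
|---|---|---|
| PASI 100 at Week 16 (primary) | composite | no |
| Time to PASI 100 (key secondary) | competing risk | no |
| PASI 90, PASI 100, IGA and DLQI responses at Week 28 | composite | no |
| Change in SF-36v2 PCS, MCS at Week 28 (secondary) | treatment-policy | yes |
| Absolute PASI at Week 28 (exploratory) | treatment-policy | yes |

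Pruritus and pain change at Week 28 are also treatment-policy, but come from the daily home eDiary, so the visit list bears on them less directly. The treatment-policy supplementary estimand for the primary endpoint is at Week 16, which the minimum set protects.

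**2. Design figure.** The point rests on no stated figure. As a check, the protocol's transition intensities give Week 16 rates of 0.341 and 0.163, and an exact two-sided Fisher test with 120 per arm then has power 86.9%, against 87.0% in Panel 20. Power concerns Week 16 PASI 100 and time to PASI 100, so nothing there changes.

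**3. Number of subjects, on assumptions.** The term no response is not defined and attendance after stopping is not forecast. Assume that 5% to 21.8% of an arm stop and that 25% to 100% of those miss Week 28. The upper share is 100% − 78.2%, those below PASI 75 at Week 16 in protocol Panel 17 (brodalumab rescue data with non-responder imputation), used only as a wide limit.

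- Low: 120 × 0.05 × 0.25 = 1.5 subjects per arm.
- High: 120 × 0.218 × 1.00 = 26 subjects per arm.

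**4. Bias in one arm mean** = missing share × imputation error. With an assumed absolute PASI error of 1 to 5 points:

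- Low: 0.05 × 0.25 × 1 = 0.01 points.
- High: 0.218 × 1.00 × 5 = 1.1 points.

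**5. Bias in the treatment difference**, with a common error = (missing share in one arm − missing share in the other) × error:

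- SF-36v2, 12% against 4%, error 5: 0.08 × 5 = 0.4; error 10: 0.08 × 10 = 0.8.
- Absolute PASI, 20% against 10%, error 1 to 5: 0.10 × 1 = 0.1 to 0.10 × 5 = 0.5.
- Equal shares and equal errors: 0.

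The error can have either sign, so each figure can act in either direction.

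**6. Comparison with the planned sensitivity analysis.** SAP Panel 13 sets SF-36v2 margins of ±6, ±12 and ±18. At the same 8-point imbalance these move the difference by 0.08 × 6 = 0.48 to 0.08 × 18 = 1.44, which extends beyond the 0.4 to 0.8 in step 5.

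**The case against.** The strongest reply is that Week 28 is already requested. Section 10.1 asks for all remaining visits, Section 10.3 encourages them before it offers the fallback, Section 7.3 defines trial completion regardless of stopping IMP, and Appendix 6 treats Week 28 as critical together with Week 16. This stands in part: a reader who takes Section 10.3 alone might infer that late stoppers need attend only the early termination visit, and the documents do not say that. It does not remove the gap, because the smaller set is offered as an explicit alternative.

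A reader might also infer that the missing values will lie mainly in subjects stopped for no response, that MAR imputation is too favourable for them, and that a real difference would shrink. The documents support none of these:

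- No figure ties missing Week 28 values to that reason. Subjects who stop before Week 16 also have no Week 28 visit in their minimum set.
- Section 9.5 provides for other treatment options after stopping, so a subject may do better by Week 28 than the model predicts. In Panel 17, inadequate responders to ustekinumab went from 0% to 41.1% PASI 100 at Week 28 after starting brodalumab.
- Imputation conditions on the subject's own two preceding scores (SAP Section 5.4.1), so a poor Week 16 value already lowers the prediction.
- Panel 17 missing counts rise from 9 of 124 (7.3%) at Week 16 to 14 of 124 (11.3%) at Week 28, but they come from other trials, cover all causes and are not monotone (12 at Week 20, 11 at Week 24).

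The delta-adjusted analysis spans errors of the sizes assumed above. That also stands, although it shows sensitivity and does not replace observed values.

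Finally, SAP Section 6 reports that no event time was censored other than administratively. This does not settle the point: stopping IMP independently of pandemic restrictions is a competing event, so later absence would not appear as censoring.

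**Conclusion.** The point holds as a gap between data collection and estimand. Week 28 is requested but not protected as a minimum, while change in SF-36v2 PCS and MCS (secondary) and absolute PASI (exploratory) at Week 28 are defined so that off-treatment values count. With MAR imputation within arm and the retrieved-data analysis dropped, missing values there rest on the imputation model and one common delta.

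The direction and size of any bias cannot be determined from the documents. The figures of 0.4 to 0.8 SF-36v2 points and 0.1 to 0.5 PASI points rest wholly on assumed missing shares and errors, and the bias is zero when both are equal across arms. The primary, key secondary and binary composite endpoints, and the sample size, are unaffected by this gap. It is a minor but specific improvement.

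**What to change.** In protocol Section 10.3 and in note 2 to Panels 2 and 3, add the Week 28 visit, with at least SF-36v2, PASI and AEs, to the minimum set for every subject who permanently discontinues IMP, before or after Week 16. In note 3 to Panel 29, name Week 28 alongside Week 16 for the assessments that the reduced schedule contains. That schedule has PASI and AEs but no SF-36v2. IGA and DLQI need not be added for this purpose, because values after discontinuation independent of pandemic restrictions do not enter their Week 28 endpoints.

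The cost is protocol wording and one already scheduled visit for the few discontinued subjects who would otherwise skip it. No dose, stopping rule, sample size or analysis model changes. The SAP was written after blind review and records an early end of the trial, so the change helps only where Week 28 visits are still to come.
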